## 7 STUDY SCHEDULE

Study visit information is listed in this section, Section 8, and the Schedule of Events (Appendix A). Further instructions are described in the protocol-specific MOP.

### 7.1 Visit 1 – Screening and Enrollment/Baseline Visit (Day 1)

- The potential subject will be provided with a description of the study (purpose and study procedures) and asked to read the ICF or have it read to him/her. The ICF must be signed before any screening or study procedures are performed.
- Demographic information will be collected from the subject.
- Eligibility criteria will be reviewed with the subject.
  - Complete medical history will be obtained by interviewing subjects (and reviewing medical records for the past 14 days, if available) to assure eligibility. If available in the medical record, the most recent viral load result from the past six months prior to enrollment should be recorded.
  - Sexual history for the past 60 days will be collected.
  - A targeted physical examination will be performed by a qualified study clinician (including vital signs: temperature, heart rate, respiration rate, and blood pressure; and genital, rectal, oral, skin, and lymph node examinations).
  - Study staff will swab consenting subjects' oral cavities and primary or secondary lesions (if lesions are present per Section 5.1); see Section 8.2.2.
  - A urine or serum pregnancy test will be performed on all subjects of childbearing potential and must be negative prior to randomization.
  - All concomitant medications taken in the last 30 days prior to initiating BPG treatment will be recorded on the appropriate data collection form.
  - Blood will be collected for RPR test, storage, and HIV assays (including a CD4 count for persons with known HIV infection whose medical records do not include a CD4 count in the past 30 days, and an HIV test for persons who do not have a previously documented positive HIV test result). Specimens will be collected at sites of exposure for screening/diagnosis of gonorrhea and chlamydia for all subjects who have not been tested since last sexual activity and for all subjects who have been sexually active in the past 14 days and for other STIs as indicated by local standard of care and subject history. Clinicians will provide pre- and post-test counseling, treatment, and referrals per local standard of care.

At this juncture, if a potential subject is not eligible, the reason for screening failure will be recorded and the subject will not be enrolled.

- 
- Subject will be enrolled in Advantage eClinical® and randomly assigned to Arm 1 or Arm 2.
  - BPG will be administered, and the subject will be observed per clinic standard operating procedure (SOP).
  - Study personnel will discuss with subjects and assess and record all AEs/SAEs (including solicited reactogenicity AEs and other unsolicited AEs).
  - Protocol requirements will be reviewed with the subject.
  - Contact information will be collected, the subject's preferred method of contact will be noted, and the Week 1 visit will be scheduled.
  - The Jarisch-Herxheimer checklist will be distributed and the instructions reviewed with the subject. The subject will be asked to have the completed checklist available for reference during the non-visit contact approximately 24-48 hours after Visit 1 and to bring it to Visit 2. Study personnel will instruct the subject to use a thermometer to take temperature reading(s) at home, if possible, and note the highest temperature if s/he feels feverish any time before being contacted to assess for symptoms of a Jarisch-Herxheimer reaction as described in Section 8.1. Study personnel will attempt to contact subjects by phone call, text message, or email approximately 24 hours after Visit 1 to make this assessment. Note that data will be recorded on the appropriate electronic case report forms (eCRFs) based on subject interview; the Jarisch-Herxheimer checklist completed by the subject will not be retained.

## 7.2 Follow-up

### 7.2.1 Visit 2 – Week 1 (Day 7 to 13)

- Subject will be evaluated for resolution of any clinical signs of infection and will be asked specific questions on medication tolerance. If the subject was not contacted following Visit 1, s/he will be evaluated for symptoms of a Jarisch-Herxheimer reaction at Visit 2 as described in Section 8.1.
- Medical history will be reviewed (including review of interval medical records and local laboratory results, if available) and updated as appropriate. If available in the medical record, the most recent viral load result since enrollment should be recorded. If the local laboratory results indicate a need for retreatment for syphilis infection, the subject will receive treatment according to the local clinic's standard protocols and will be withdrawn from the study per protocol Section 5.3.3.
- Interim sexual history since the last study visit will be collected. Specimens will be collected at sites of exposure for STI screening/diagnosis as indicated by local standard of care and subject history.

- 
- A urine pregnancy test will be performed on all subjects of childbearing potential.
  - All concomitant medications taken since the last study visit will be recorded on the appropriate data collection form. Previously recorded medications will be updated as appropriate.
  - A targeted physical examination will be performed by a qualified study clinician (including vital signs: temperature, heart rate, respiration rate, and blood pressure; and genital, rectal, oral, skin, and lymph node examinations).
  - Blood will be collected for follow-up RPR tests and storage.
  - Arm 2 only: second dose of BPG will be administered, and the subject will be observed per clinic SOP.
  - Study personnel will discuss with subjects and assess and record all AEs/SAEs (including solicited reactogenicity AEs and other unsolicited AEs).
  - Contact information will be reviewed, and the Week 2 visit will be scheduled.

### **7.2.2 Visit 3 – Week 2 (6 to 12 days after Visit 2)**

- Subject will be evaluated for resolution of any clinical signs of infection.
- Medical history will be reviewed (including review of interval medical records and local laboratory results, if available) and updated as appropriate. If available in the medical record, the most recent viral load result since enrollment should be recorded. If the local laboratory results indicate a need for retreatment for syphilis infection, the subject will receive treatment according to the local clinic's standard protocols and will be withdrawn from the study per protocol Section 5.3.3.
- Interim sexual history since the last study visit will be collected. Specimens will be collected at sites of exposure for STI screening/diagnosis as indicated by local standard of care and subject history.
- A urine pregnancy test will be performed on all subjects of childbearing potential.
- All concomitant medications taken since the last study visit will be recorded on the appropriate data collection form. Previously recorded medications will be updated as appropriate.
- A targeted physical examination will be performed by a qualified study clinician (including vital signs: temperature, heart rate, respiration rate, and blood pressure; and genital, rectal, oral, skin, and lymph node examinations).
- Blood will be collected for follow-up RPR tests and storage.

- 
- Arm 2 only: third dose of BPG will be administered, and the subject will be observed per clinic SOP.
  - Study personnel will discuss with subjects and assess and record all AEs/SAEs (including solicited reactogenicity AEs and other unsolicited AEs).
  - Contact information will be reviewed, and the Month 1 visit will be scheduled.

### **7.2.3 Visit 4 – Month 1 (Day 30 ± 7 days)**

- Medical history will be reviewed (including review of interval medical records and local laboratory results, if available) and updated as appropriate. If available in the medical record, the most recent viral load result since enrollment should be recorded. If the local laboratory results indicate a need for retreatment for syphilis infection, the subject will receive treatment according to the local clinic's standard protocols and will be withdrawn from the study per protocol Section 5.3.3.
- Interim sexual history since the last study visit will be collected. Specimens will be collected at sites of exposure for STI screening/diagnosis as indicated by local standard of care and subject history.
- A urine pregnancy test will be performed on all subjects of childbearing potential.
- All concomitant medications taken since the last study visit will be recorded on the appropriate data collection form. Previously recorded medications will be updated as appropriate.
- Study personnel will discuss with subjects and assess and record all AEs/SAEs (including solicited reactogenicity AEs and other unsolicited AEs).
- A targeted physical examination will be performed by a qualified study clinician (including vital signs: temperature, heart rate, respiration rate, and blood pressure; and genital, rectal, oral, skin, and lymph node examinations).
- Blood will be collected for follow-up RPR tests, storage, and CD4 counts on persons newly found to have HIV infection from Visit 1 to Visit 4 (inclusive) whose medical records do not include a CD4 count in the past 30 days. Clinicians will provide pre- and post-test counseling, treatment, and referrals per local standard of care.
- Contact information will be reviewed, and the Month 3 visit will be scheduled.

### **7.2.4 Visit 5 – Month 3 (Day 90 ± 21 days)**

- Medical history will be reviewed (including review of interval medical records and local laboratory results, if available) and updated as appropriate. If the local laboratory results indicate a need for retreatment for syphilis infection, the subject will receive treatment

---

according to the local clinic's standard protocols and will be withdrawn from the study per protocol Section 5.3.3.

- Interim sexual history since the last study visit will be collected. Specimens will be collected at sites of exposure for STI screening/diagnosis as indicated by local standard of care and subject history.
- A urine pregnancy test will be performed on all subjects of childbearing potential.
- All concomitant medications taken since the last study visit will be recorded on the appropriate data collection form. Previously recorded medications will be updated as appropriate.
- A targeted physical examination will be performed by a qualified study clinician (including vital signs: temperature, heart rate, respiration rate, and blood pressure; and genital, rectal, oral, skin, and lymph node examinations).
- HIV testing will be performed if the subject was previously noted to be HIV-uninfected. Clinicians will provide pre- and post-test counseling, treatment, and referrals per local standard of care.
- Blood will be collected for follow-up RPR tests and storage.
- Contact information will be reviewed, and the Month 6 visit will be scheduled.

### **7.2.5 Visit 6 – Month 6 (Day 180 ± 21 days)**

- Medical history will be reviewed (including review of interval medical records and local laboratory results, if available) and updated as appropriate. If the local laboratory results indicate a need for retreatment for syphilis infection, the subject will receive treatment according to the local clinic's standard protocols and will be withdrawn from the study per protocol Section 5.3.3.
- Interim sexual history since the last study visit will be collected. Specimens will be collected at sites of exposure for STI screening/diagnosis as indicated by local standard of care and subject history.
- A urine pregnancy test will be performed on all subjects of childbearing potential.
- All concomitant medications taken since the last study visit will be recorded on the appropriate data collection form. Previously recorded medications will be updated as appropriate.
- A targeted physical examination will be performed by a qualified study clinician (including vital signs: temperature, heart rate, respiration rate, and blood pressure; and genital, rectal, oral, skin, and lymph node examinations).
- HIV testing will be performed if the subject was previously noted to be HIV-uninfected.

Clinicians will provide pre- and post-test counseling, treatment, and referrals per local standard of care.

- Blood will be collected for follow-up RPR tests, storage, and CD4 counts on persons found to have HIV infection whose medical records do not include a CD4 count in the past 30 days.
- Contact information will be reviewed, and the Month 9 visit will be scheduled.

### **7.2.6 Visit 7 – Month 9 (Day 270 ± 28 days)**

- Medical history will be reviewed (including review of interval medical records and local laboratory results, if available) and updated as appropriate. If the local laboratory results indicate a need for retreatment for syphilis infection, the subject will receive treatment according to the local clinic's standard protocols and will be withdrawn from the study per protocol Section 5.3.3.
- Interim sexual history since the last study visit will be collected. Specimens will be collected at sites of exposure for STI screening/diagnosis as indicated by local standard of care and subject history.
- A urine pregnancy test will be performed on all subjects of childbearing potential.
- All concomitant medications taken since the last study visit will be recorded on the appropriate data collection form. Previously recorded medications will be updated as appropriate.
- A targeted physical examination will be performed by a qualified study clinician (including vital signs: temperature, heart rate, respiration rate, and blood pressure; and genital, rectal, oral, skin, and lymph node examinations).
- HIV testing will be performed if the subject was previously noted to be HIV-uninfected. Clinicians will provide pre- and post-test counseling, treatment, and referrals per local standard of care.
- Blood will be collected for follow-up RPR tests and storage.
- Contact information will be reviewed, and the Month 12 visit will be scheduled.

### **7.2.7 Visit 8 – Month 12 (Day 360 ± 28 days) (Final Study Visit)**

- Medical history will be reviewed (including review of interval medical records and local laboratory results, if available) and updated as appropriate. If the local laboratory results indicate a need for retreatment for syphilis infection, the subject will receive treatment according to the local clinic's standard protocols.
- Interim sexual history since the last study visit will be collected. Specimens will be

---

collected at sites of exposure for STI screening/diagnosis as indicated by local standard of care and subject history.

- A urine pregnancy test will be performed on all subjects of childbearing potential.
- All concomitant medications taken since the last study visit will be recorded on the appropriate data collection form. Previously recorded medications will be updated as appropriate.
- A targeted physical examination will be performed by a qualified study clinician (including vital signs: temperature, heart rate, respiration rate, and blood pressure; and genital, rectal, oral, skin, and lymph node examinations).
- HIV testing will be performed if the subject was previously noted to be HIV-uninfected. Clinicians will provide pre- and post-test counseling, treatment, and referrals per local standard of care.
- Blood will be collected for follow-up RPR tests, storage, and CD4 counts on persons found to have HIV infection whose medical records do not include a CD4 count in the past 30 days.
- Contact information will be reviewed.

### **7.3 Early Termination Visit**

The Visit 8 assessments and eCRFs (see Section 7.2.7: Visit 8 – Month 12 (Final Study Visit)) must be completed at the end of each subject's participation in the study if discontinued prior to Visit 8. If a subject withdraws between scheduled visits, the subject must come to the clinic to perform the Visit 8 assessments.

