#### **5.3.4 Handling of Withdrawals from Study Participation/Discontinuations of Study Treatment**

Subjects who withdraw from study participation, or are excluded from any efficacy endpoint analysis, or are lost to follow-up after signing the informed consent form (ICF), randomization, and receipt of the first dose of BPG will not be replaced. Subjects who withdraw consent after signing the ICF and randomization but before receipt of the first dose of BPG may be replaced.

If the subject requests to discontinue study treatment at any time after the first dose of BPG, the subject will be asked to continue scheduled study procedures including safety and efficacy evaluations, if possible, and be given appropriate care under medical supervision if symptoms of any AE related to participation in the study are continuing. The subject will be followed until the AE is resolved or until the subject's condition becomes stable.

Subjects who request to discontinue study treatment at any time after the first dose of BPG will be reminded of the importance of continuing in the study for safety evaluations. Subjects will be encouraged to complete the Early Termination Visit if they choose not to complete the remaining study visits (i.e., if they withdraw from study participation). The Early Termination Visit procedures are listed in Section 7.3. Subjects who choose to withdraw from study participation will no longer be contacted for follow-up.

In the case of subjects who fail to appear for a follow-up safety assessment, extensive effort (e.g., three documented contact attempts via phone calls, e-mails, etc., made on separate occasions and followed by a certified letter) will be made to locate or recall them, or at least to determine their health status. Subjects who cannot be located after extensive effort will no longer be contacted for follow-up. These efforts will be documented in the subject's records.

If a subject is withdrawn from the study due to an AE that prohibits continued participation in the study, s/he will be given appropriate care and treatment under medical supervision until the condition has resolved or becomes stable.

Safety and efficacy data will be collected on any subject who is excluded from any efficacy endpoint analysis. Refer to Section 11 for details on how subjects who are withdrawn will be handled during analysis.

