## **9 ASSESSMENT OF SAFETY**

### **9.1 Specification of Safety Parameters**

Safety will be monitored throughout the study by physical examination (including vital signs: temperature, heart rate, respiration rate, and blood pressure; and genital, rectal, oral, skin, and lymph node examinations) and subject reporting. Safety will be assessed by the frequency and severity of AEs/SAEs (including solicited reactogenicity AEs and other unsolicited AEs) occurring from the time of study product administration through the Month 1 visit.

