**APPENDIX A: SCHEDULE OF EVENTS**

Procedures		Visit 1 – Screening/ Enrollment (Day 1)	Contact (approx. 24 hours after Visit 1)	Visit 2 (Week 1 – Day 7 to 13)	Visit 3 (Week 2 – 6 to 12 days after Visit 2)	Visit 4 (Month 1 – Day 30 ± 7 days)	Visit 5 (Month 3 – Day 90 ± 21 days)	Visit 6 (Month 6 – Day 180 ± 21 days)	Visit 7 (Month 9 – Day 270 ± 28 days)	Visit 8 (Month 12 – Day 360 ± 28 days)	Early Termination	Unscheduled Visit 
Informed consent		X										
Demographics		X										
Eligibility criteria		X										
Medical history 		X		X	X	X	X	X	X	X	X	X
Sexual history 		X		X	X	X	X	X	X	X	X	X
Targeted physical exam 		X		X	X	X	X	X	X	X	X	X
Pregnancy test 		(X)		(X)	(X)	(X)	(X)	(X)	(X)	(X)	(X)	(X)
Concomitant medications 		X		X	X	X	X	X	X	X	X	X
Specimen collection	RPR titer	X		X	X	X	X	X	X	X	X	
	Storage	X		X	X	X	X	X	X	X	X	
	CD4 count 	(X)				(X)		(X)		(X)	(X)	
	HIV testing 	(X)					(X)	(X)	(X)	(X)	(X)	
	Other STI screening/ diagnosis 	X		(X)	(X)	(X)	(X)	(X)	(X)	(X)	(X)	(X)
	Oral cavity and lesions (if present) swabbed 	(X)		(X)	(X)	(X)	(X)	(X)	(X)	(X)	(X)	(X)
Randomization		X										
BPG administered 		X		(X)	(X)							
Contact information collected/reviewed 		X		X	X	X	X	X	X	X	X	X
Jarisch-Herxheimer checklist 		X	X	(X)								
Jarisch-Herxheimer reaction assessed 			X	(X)								
Resolution of syphilis signs assessed				X	X							
AEs/SAEs assessed 		X		X	X	X						X

(X) – As indicated/appropriate. Refer to footnotes below and protocol Section 7.

 At Visit 1, collect complete medical history (including review of medical records for the past 14 days, if available). At subsequent visits, review medical history (including interval medical records, if available) and update as appropriate.

 At Visit 1, collect sexual history for the past 60 days. At subsequent visits, collect interim sexual history since last visit.

 Targeted physical exam includes vital signs: temperature, heart rate, respiration rate, and blood pressure; and genital, rectal, oral, skin, and lymph node examinations.

 Perform on subjects of childbearing potential. At Visit 1, urine or serum pregnancy test is permitted. At subsequent visits, perform urine pregnancy test.

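### An Early Termination Visit held before Month 1 has no scheduled AE/SAE assessment, and the Visit 3 and Visit 4 windows overlap

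*Protocol*

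**What the plan says.** **Exit visit.** Protocol Section 7.3 takes both the assessments and the eCRFs of the Early Termination Visit from Visit 8, and says of someone who leaves between visits: "If a subject withdraws between scheduled visits, the subject must come to the clinic to perform the Visit 8 assessments". The Visit 8 list in Section 7.2.7 covers medical and sexual history, pregnancy test, concomitant medications, targeted examination, HIV test, blood draws and contact details. It has no AE or SAE item. In Appendix A the row "AEs/SAEs assessed" is marked at Visits 1 to 4 and Unscheduled, and is blank at Visits 5 to 8 and Early Termination.

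**AE period.** Section 9.1 assesses safety by AEs and SAEs, solicited reactions included, "occurring from the time of study product administration through the Month 1 visit". Sections 4 and 9.4 give the same end point. Section 9.2.1 goes further and requires every AE during study participation to be documented.

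**Windows.** Visit 2 is Day 7 to 13 (Section 7.2.1). Visit 3, with the third dose in Arm 2, is 6 to 12 days after Visit 2 (Section 7.2.2). Visit 4, the last scheduled visit with an AE assessment, is Day 30 ± 7 (Section 7.2.3).

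**The concern.** Leaving AEs out of Visit 8 makes sense at Month 12, long after AE collection has ended. Section 7.3 carries the same list back to any exit date, including one inside the AE period. A site that follows the schedule as written does not ask about AEs or injection-site reactions at that subject's last visit.

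The subject stays in the safety population, which is everyone randomized who received at least one dose (Sections 11.4.1 and 11.4.3). An event not elicited is therefore tabulated as no event. This is a gap in data collection, and no analysis plan can repair it.

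The visit windows raise a related question: how long AEs are observed after the third dose when Visit 3 is late and Visit 4 early.

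**Working it through.** **1. Is the blank cell a slip in the table?** No. In Appendix A the Early Termination column matches the Visit 8 column row by row, and Section 7.3 orders exactly that. Text and table agree with each other. Both disagree with the AE period when the exit comes before Month 1.

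**2. What each kind of early leaver gets** (Sections 7.1 to 7.3, Appendix A):
- Leaves after Visit 1 and before Visit 2: the Day 1 AE assessment and the Jarisch-Herxheimer contact at about 24 hours. No AE item at Early Termination.
- Arm 2, leaves after Visit 3 and before Visit 4: the AE item at Visit 3 itself, listed after the dose. No scheduled AE assessment after that day.
- Leaves after Visit 4: nothing is lost, because the AE period has closed for everyone.
- Lost to follow-up: no exit visit takes place, so its content does not matter.

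The gap is therefore confined to subjects who leave between visits, before Month 1, and attend the exit visit. The protocol gives no rate for this group. Section 7.3 makes attendance mandatory while Section 5.3.4 only encourages it, so the share attending cannot be derived either.

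**3. Window arithmetic.**
- Visit 3 earliest: 7 + 6 = Day 13. Latest: 13 + 12 = Day 25.
- Visit 4: 30 − 7 = Day 23 to 30 + 7 = Day 37.
- Overlap: Days 23 to 25.
- Longest time from third dose to Visit 4: 37 − 13 = 24 days.
- Shortest: 23 − 25 = −2 on the windows alone, hence 0 days if Visit 4 cannot precede Visit 3.
- Third dose on Day 25: 0 to 37 − 25 = 12 days, or 30 − 25 = 5 days with Visit 4 on Day 30.
- Nominal timing, third dose on Day 15 and Visit 4 on Day 30: 15 days.
- Arm 1, from its only dose on Day 1: 23 − 1 = 22 to 37 − 1 = 36 days.

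Visit 2 has 7 permitted days and the gap to Visit 3 has 7 permitted lengths, giving 7 × 7 = 49 pairs. Of these, 6 put Visit 3 on Day 23 or later: Day 11 + 12; Day 12 + 11 or 12; Day 13 + 10, 11 or 12. This counts permitted dates and is not a probability.

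**The case against.** The strongest reply is that the exit visit is not silent on events. It includes a history update with record review, new medications, vital signs and an examination (Section 7.2.7). Section 8.1 takes the interim history by interview, and Section 9.2.1 would require an AE found this way to be documented. That stands: what is missing is the scheduled AE/SAE and solicited-reaction assessment, not all contact. But an interim history is not the graded, causality-assessed collection of Sections 9.2.1 and 9.2.2, and the AE item at Unscheduled Visits (Section 7.4) is at the site investigator's discretion.

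A reader might infer that events are lost selectively in those who had them. The documents do not support this. Subjects who ask to stop treatment are asked to stay on schedule, where AEs are assessed. For the case "If a subject is withdrawn from the study due to an AE that prohibits continued participation in the study", Section 5.3.4 provides care until the condition resolves or is stable, so that event is already known. Pregnancy and retreatment mostly come to light at Visits 2 to 4, which have an AE item. SAEs must be reported within 24 hours of site awareness (Section 9.3.1).

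A reader might also want AE collection to end at a set interval after the last dose. Both arms now share one period from Day 1 and the same AE visits. A last-dose rule would lengthen the period in Arm 2 only and make ascertainment unequal. That is a debatable trade-off, not an error in the plan.

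Finally, little rests on these tables. Section 9.2.1 calls the safety profile of one and three doses well established, and the Jarisch-Herxheimer outcome has its own contact. This limits the weight of the point but does not remove the contradiction.

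**Conclusion.** The point holds in a narrow form. For exits between visits before Month 1, the schedule as written omits an AE/SAE and solicited-reaction assessment that Sections 4, 9.1 and 9.2.1 call for. The result is incomplete safety ascertainment in what is probably a small group. Any unrecorded event would lower the tabulated AE rate.

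A reader might try to size this by applying an assumed early-exit rate to the 560 enrolled, or by turning that rate into percentage points of AE incidence. The documents support neither. They give no exit rate before Month 1, not every leaver attends the visit, and such an upper bound would need every leaver to have had an event that no earlier visit recorded.

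The window overlap on Days 23 to 25 is a matter of arithmetic. Observation after the third dose can run from 0 to 24 days in window. The low end needs a late Visit 3 and a Visit 4 at the start of its window; nominal timing gives 15 days. Efficacy conclusions and sample size are unaffected.

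**What to change.** - In Section 7.3, state that an Early Termination Visit held before the Month 1 visit includes the AE/SAE assessment, solicited reactions included.
- In Appendix A, add a conditional mark in the Early Termination column of the AE/SAE row, with a footnote giving the same limit.
- The sponsor must reconcile the Visit 3 and Visit 4 windows in Sections 7.2.2 and 7.2.3 and Appendix A. Which window to change is for the sponsor to decide.

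The first two changes cost one sentence, one schedule mark with its footnote, and making an existing eCRF available at one more visit. They add no visits, and the end of the AE period stays at the Month 1 visit for both arms.
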